7 INVESTIGATIONAL MEDICINAL PRODUCT

7.1 DESCRIPTION OF INVESTIGATIONAL MEDICINAL PRODUCT

Duvelisib drug substance is a white to off-white crystalline powder. The duvelisib drug product is formulated with excipients (Diluent, glidant, disintegrant, and lubricant) that are listed in Food and Drug Administration's (FDA) Inactive Ingredients Database for approved drug products and/or Generally Regarded as Safe (GRAS) in two different capsule strengths (5 mg and 25 mg) for oral delivery.

7.2 DOSAGE AND ADMINISTRATION

7.2.1 Dosage

7.2.1.1 *Duvelisib*

Duvelisib will be administered daily in 28-day cycles (with the exception of Cycle 1 which is 21 days). Duvelisib is administered orally as a capsule formulation and will be supplied by the Sponsor. Duvelisib will be administered as a fixed dose in mg/day and should be administered using the minimal number of capsules necessary.

For an individual subject, dose reductions and discontinuations may be based on the clinical judgment of the Investigator with notification to the Medical Monitor/Sponsor (see [Section 4.2.1.1](#)).

7.2.1.2 *Ofatumumab*

Subjects randomized to ofatumumab will receive treatment consistent with the approved product labeling: an initial IV dose of 300 mg ofatumumab on Day 1 followed by seven weekly doses of 2000 mg. Thereafter, subjects will receive 2000 mg ofatumumab once every month for four months through Cycle 7 or until disease progression or unacceptable toxicity (whichever comes first), as outlined in the schedule of assessments. Administration of ofatumumab will not exceed the 12 doses (within 7 cycles) as described in the prescribing information. For an individual subject, dose reductions (see [Table 10](#)) and discontinuations may be based on the clinical judgment of the Investigator with notification to the Medical Monitor/Sponsor.

7.2.2 Administration

7.2.2.1 *Duvelisib*

Duvelisib should be taken daily BID (every 12 ±2 hours) in 28-day cycles. Cycle 1 is a 21-day cycle.

On Cycle 2 Day 1, the morning dose of study medication will be administered in the clinic to accommodate PK sample collection. An attempt should be made to enable each dose to be

taken at approximately the same time of day. Missed doses outside the windows defined above or vomited doses should not be taken or repeated.

Duvelisib doses will be dispensed to the subject so that the subject has enough duvelisib doses until at least the next dispensation visit, taking into account the dispensation visit window.

Duvelisib capsules should be swallowed whole with a glass of water (approximately 8 ounces or 240 mL) at approximately the same time(s) each day. Subjects must avoid grapefruit and grapefruit juice.

Duvelisib may be administered without regard to meals.

7.2.2.2 Ofatumumab

Ofatumumab will be administered via infusion, as described in the ofatumumab (ARZERRA®) package insert.^{10, 11} Please refer to the country-specific package insert for more details.

7.3 PACKAGING AND LABELING

Duvelisib will be supplied to the clinical trial site as open-label medication. Please refer to the IPI-145-07 Pharmacy Manual for details regarding packaging and labeling of Investigational Product.

7.4 STORAGE AND HANDLING

7.4.1 Duvelisib

Duvelisib must be stored at room temperature (15 to 30°C).

Caution is required when handling duvelisib. Pharmacists should follow standard procedures for the handling of investigational drugs, including avoidance of eye or skin contact with the drug product. If there is exposure to the drug product, provide treatment as necessary for physical exposure (skin washing) or inhalation (move to fresh air) and seek medical advice as necessary.

When duvelisib capsules are distributed for self-administration, they should only be handled by the study subject. After handling capsules, the subject should wash their hands thoroughly. If someone who is not enrolled in a clinical trial involving duvelisib swallows a capsule or inhales drug powder from a broken capsule of duvelisib, they should contact the relevant Principal Investigator to determine whether safety monitoring is necessary. Capsules should always be stored in the container provided to the study subject. Refer to [Section 8.2.3.2](#) for details on reporting any exposure.

7.4.2 Ofatumumab

Ofatumumab (ARZERRA®) is supplied as a sterile, clear to opalescent, colorless, preservative-free liquid concentrate (20 mg/mL) for dilution and intravenous administration provided in single-use glass vials with a latex-free rubber stopper and an aluminum over seal.

Each vial contains either 100 mg ofatumumab in 5 mL of solution or 1,000 mg ofatumumab in 50 mL of solution.

Store ARZERRA[®] refrigerated between 2° to 8°C (36° to 46°F). Do not freeze. Vials should be protected from light.

See ARZERRA[®] package insert for more details.^{10, 11}

7.5 INVESTIGATIONAL MEDICINAL PRODUCT ACCOUNTABILITY

7.5.1 Duvelisib

The Investigator or designee is responsible for taking an inventory of each shipment of duvelisib investigational supplies received, and comparing it with the accompanying drug accountability form.

All unused duvelisib will be retained at the site. After full drug accountability and reconciliation, the Investigator will dispose of the study drug at the clinical trial site according to site procedures, or at the Sponsor's request will return all duvelisib to the Sponsor, or its designee. If any study drug is lost or damaged, the disposition of the study drug should be documented.

Subjects should be instructed to bring all unused duvelisib to each study visit. The study site should count all capsules that the subject returns, and should take account for taken doses, missed doses, doses reduced due to missing or lost capsules, etc., before dispensing new study drug to the subject. Any subject who does not take the prescribed dose should be requested to return the remaining drug to the clinical trial site for accountability.

7.5.2 Ofatumumab

For Sponsor supplied Ofatumumab, the Investigator or designee is responsible for taking an inventory of each shipment received, and comparing it with the accompanying drug order form.

All unused Ofatumumab will be retained at the site. After full drug accountability and reconciliation, the Investigator will dispose of the study drug at the clinical trial site according to site procedures, or at the Sponsor's request will return all ofatumumab to the Sponsor, or its designee. If any study drug is lost or damaged, the disposition of the study drug should be documented.

7.6 ASSIGNMENT TO TREATMENT

Once a subject has met all entry criteria, the IRT will be used to generate a distinct subject identifier. Eligible subjects will be randomized within 7 days prior to receipt of first dose of study drug. If a subject discontinues from the study, the subject identifier will not be reused and the subject will not be allowed to re-enter the study.

Eligible subjects will be randomized via IRT in a 1:1 ratio to one of two treatment arms:

- Arm 1: Duvelisib 25 mg BID

- Arm 2: Ofatumumab

In order to ensure subject balance between treatment groups, study subjects will be stratified by the following:

- High risk cytogenetics (presence vs absence of del[17p])
- Refractory/early relapse to purine analog based treatment (progression <12 months after fludarabine/pentostatin: yes vs no)
- Grade 4 cytopenia(s) (presence vs absence of neutropenia or thrombocytopenia at baseline)

Randomization is to occur within 7 days of first dose after all screening assessments have been completed.

7.7 ASSESSMENT OF COMPLIANCE

7.7.1 Duvelisib

At each applicable visit, doses will be dispensed to the subject so that the subject will have enough doses until the next applicable visit, taking into account the window for that subsequent visit. Compliance for doses taken outside of the clinic will be assessed by a count of the capsules returned to the study trial site by the subject and review with the subject.

7.7.2 Ofatumumab

Ofatumumab will be administered via infusion as described in the package insert by the test article administrator.

7.8 TREATMENT OF OVERDOSE

In the case of overdose, clinic staff should be notified immediately and supportive care is to be given as indicated. Subjects should be informed to contact their doctor immediately if they have taken an overdose and should stop taking duvelisib.

No data is available regarding overdosage with ofatumumab. Supportive care is to be given as indicated in the event of an ofatumumab overdosage.

8 ADVERSE EVENTS AND SERIOUS ADVERSE EVENTS

8.1 DEFINITIONS

The definitions of AEs and SAEs are provided below.

8.1.1 Adverse Event

An AE is any untoward medical occurrence associated with the use of a drug or with study participation, regardless of the relationship of the occurrence to study drug or protocol. An AE can be any unfavorable and unintended sign (including an abnormal laboratory finding), symptom or disease temporally associated with the use of the drug, whether or not considered related to the drug. An AE can arise from any use of the drug, and from any route of administration, formulation or dose, including an overdose.

Medical conditions present prior to the initiation of the study, as well as ongoing changes in laboratory values/conditions that are being treated at baseline, will be captured as an AE if the condition worsens.

8.1.2 Adverse Reactions and Suspected Adverse Reactions

All noxious and unintended responses to a medicinal product related to any dose should be considered adverse drug reactions. Suspected adverse reactions are any adverse events for which there is a reasonable possibility that the drug caused the adverse event. Adverse reactions also include medication errors and uses outside of what is foreseen in the protocol, which may include misuse, abuse, and overdose (intentional or unintentional) of the product.

8.1.3 Serious Adverse Event

An adverse event or suspected adverse reaction is considered serious if, in the view of either the investigator or Sponsor, it results in any of the following outcomes:

- Results in death
- Is immediately life-threatening
- Requires inpatient hospitalization or prolongation of existing hospitalization, unless hospitalization is for:
 - Elective or pre-planned treatment for a pre-existing condition that is unrelated to the indication under study and has not worsened since signing the ICF (as documented as medical history on the eCRF), or
 - Scheduled therapy for the target disease of the study, including admissions for transfusion support or convenience
- Results in persistent or significant disability / incapacity
- Results in congenital anomaly / birth defect.

Important medical events that may not result in death, be life-threatening, or require hospitalization, may be considered a serious adverse drug experience when, based upon

appropriate medical judgment, they may jeopardize the subject and may require medical or surgical intervention to prevent one of the outcomes listed in this definition. Examples of such medical events include allergic bronchospasm requiring intensive treatment in an emergency room or at home, blood dyscrasias or convulsions that do not result in inpatient hospitalization, or the development of drug dependency or drug abuse.

8.2 PROCEDURES FOR ELICITING, RECORDING, AND REPORTING ADVERSE EVENTS

8.2.1 Eliciting and Recording Adverse Events

Subjects will be instructed to report all AEs and will be asked a general health status question at each study visit. All AEs occurring in randomized subjects will be recorded in the eCRF from the time of ICF until 30 days after the last dose of study treatment. An AE will be followed until it is either resolved, has returned to baseline, or is determined to be a stable or chronic condition. All SAEs occurring from the signing of ICF through 30 days post last study drug will be processed as outlined in [Section 8.2.3](#).

At each required visit during the trial, all AEs that have occurred since the previous visit must be reviewed. The Investigator or appropriate designee must determine if the adverse event is serious or non-serious.

8.2.1.1 Relationship to Study Drug

The Investigator is required to provide an assessment of relationship of AEs and SAEs to study drug. A number of factors should be considered in making this assessment including: 1) the temporal relationship of the event to the administration of study drug; 2) whether an alternative etiology has been identified; and/or 3) biological plausibility. The following guidelines should be used by Investigators to assess the relationship of an AE to the administration of the study drug.

Relationship assessments that indicate the event is “Not Drug Related”:

- None: The event is related to an etiology other than the study product administration (the alternative etiology must be documented in the study subject’s medical record).
- Remote: The event is unlikely to be related to the study product and likely to be related to factors other than study product.

Relationship assessments that indicate the event is “Drug Related”:

- Possible: There is an association between the event and the administration of study drug, and there is a plausible mechanism for the event to be related to the study product; but there may also be alternative etiology, such as characteristics of the subject’s clinical status or underlying disease.
- Probable: There is an association between the event and the administration of study drug, there is a plausible mechanism for the event to be related to the study product, and the event could not be reasonably explained by known characteristics of the subject’s clinical status or an alternative etiology is not apparent.

- Definite: There is an association between the event and the administration of study drug, there is a plausible mechanism for the event to be related to the study product, and causes other than study drug have been ruled out and/or the event re-appeared on re-exposure to study drug.

8.2.1.2 Adverse event severity

The Grade of the AE will be assessed according to the NCI-CTCAE Version 4.03. Toxicities that are not specified in NCI-CTCAE Version 4.03 will be defined as follows:

- Grade 1: Mild; asymptomatic or mild symptoms; clinical or diagnostic observations only; intervention not indicated.
- Grade 2: Moderate; minimal, local or noninvasive intervention indicated; limiting age-appropriate instrumental activities of daily living (ADL).
- Grade 3: Severe or medically significant but not immediately life-threatening; hospitalization or prolongation of hospitalization indicated; disabling; limiting self-care ADL.
- Grade 4: Life-threatening consequences; urgent intervention indicated.
- Grade 5: Death related to AE.

Note: it is important to distinguish between SAEs and severe AEs. Severity is a measure of intensity, whereas seriousness is classified by the criteria based on the regulatory definitions as described in [Section 8.2.1.2](#) above.

8.2.2 Specific Instructions for Recording Adverse Events on the eCRF

8.2.2.1 Diagnosis versus Signs and Symptoms

If a diagnosis is known at the time of reporting, this should be recorded in the eCRF and/or SAE Report Form, as applicable, rather than the individual signs and symptoms (eg, record only hepatitis rather than elevated transaminases, bilirubin, jaundice). However, if a constellation of signs and/or symptoms cannot be medically characterized as a single diagnosis or syndrome at the time of reporting, each individual event should be recorded as an SAE or AE on the eCRF (and SAE Report Form, if applicable). If a diagnosis is subsequently established, it should be reported as follow-up on the eCRF (and follow up SAE report, as applicable) and should replace the individual signs and/or symptoms as the event term on the eCRF (and SAE report form, if applicable), unless the signs/symptoms are clinically significant.

8.2.2.2 Adverse Events Occurring Secondary to Other Events

In general, AEs occurring secondary to other events (eg, clinical sequelae or a cascade of events) should be identified by their primary cause. For example, if severe vomiting is known to result in dehydration, it is sufficient to record only vomiting as the SAE or AE on the eCRF (and SAE Report Form, if applicable). However, medically significant AEs occurring secondary to an initiating event that are separated in time should be recorded as independent

events on the eCRF (and SAE Report Form, if applicable). For example, if severe vomiting leads to acute renal failure, both events should be recorded on the eCRF (SAE Report Form)

8.2.2.3 Persistent or Recurrent Adverse Events

A persistent AE is one that extends continuously, without resolution, between subject evaluation time points. Such events should only be recorded once on the AE eCRF (and SAE Report Form, if applicable). If a persistent AE changes in grade, it should be recorded as a new AE on the eCRF.

A recurrent AE is one that occurs and resolves between subject evaluation time points, and subsequently recurs. All recurrent AEs should be recorded on the eCRF (and SAE Report Form if applicable).

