9.5 SAFETY ANALYSES

Safety endpoints will be summarized by treatment using the AT analysis set.

Adverse events will be coded using the Medical Dictionary for Regulatory Activities (MedDRA) version 16.1 or higher and will be graded according to the NCI-CTCAE, version 4.03 or as described in [Section 8.2.1](#).

Tabulations of treatment emergent AEs (TEAEs) by System Organ Class and Preferred Terms will be produced. A TEAE is an AE that emerges or worsens in the period from the first dose of study treatment to 30 days after the last dose of study treatment.

Separate tabulations will also be produced for drug-related adverse events, serious adverse events, events that led to treatment discontinuation, and adverse events of at least Grade 3 severity.

For laboratory tests with NCI-CTCAE grades, a shift table from baseline grade to the maximum post-baseline grade will be provided. Listings will be provided for all laboratory test results and for laboratory test results grade 3 and higher.

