#### 7.3.1 **Adverse Events**

Adverse events will be coded using MedDRA Version 16.1 or higher. The Grade of the AE will be assessed according to the NCI-CTCAE Version 4.03. If an AE is not included in the NCI-CTCAE Version 4.03, the Grade of the AE will be assessed according to the protocol, Section **8.2.1.2**.

The summary of AEs will be focused on treatment-emergent AEs. A treatment-emergent AE (TEAE) is defined as any AE that emerges or worsens in the period from the first dose of study treatment to 30 days after the last dose of study treatment. The onset date of an AE will be compared to the first dose date and the last dose date plus 30 days to determine whether the AE is treatment-emergent or not. If the onset date of an AE is completely or partially missing, refer to [Section 6.2.1](#) for the algorithm to determine whether an AE is treatment emergent.

TEAEs will be summarized for each treatment arm by MedDRA system organ class (SOC) and preferred term (PT), or PT only. For summary tables by SOC and PT, SOC will be sorted alphabetically and PT will be sorted by decreasing frequency in the duvelisib arm within each SOC. For summary tables by PT only, PT will be sorted by decreasing frequency in the duvelisib arm.

If multiple TEAEs of the same PT occur within a subject, only the maximum grade observed for this PT will be used in summary of TEAEs by grade, the subject will be counted only once in the number of subjects for this PT and only once for the number of subjects for the SOC to which this PT belongs.

An overview TEAE summary table will be provided, which will include the number of subjects with AEs in selected categories. In addition, TEAEs will be summarized for the following categories, and will be tabulated by SOC and PT, unless otherwise specified.

- Treatment-emergent AEs (All Causalities)
- Treatment-emergent AEs (Treatment-Related)
- Treatment-emergent AEs (All Causalities, by maximum grade)
- Treatment-emergent AEs (Treatment-Related, by maximum grade)
- Grade 3 or higher treatment-emergent AEs (All Causalities)
- Grade 3 or higher treatment-emergent AEs (Treatment-Related)
- Treatment-emergent SAE (All Causalities)
- Treatment-emergent SAE (Treatment-Related)
- Treatment-emergent AEs resulting in discontinuation of study drug (All Causalities)
- Treatment-emergent AEs resulting in dose hold (All Causalities)
- Treatment-emergent AEs resulting in dose reduction (All Causalities)

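### An adverse event that began before first dose and improves on treatment is counted as treatment-emergent, and a late fatal outcome has no stated link to the event that led to it

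*Protocol*

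**What the plan says.** **Recording.** Protocol 8.2.2.3 first says of a continuing event: "Such events should only be recorded once on the AE eCRF". It then makes an exception: "If a persistent AE changes in grade, it should be recorded as a new AE on the eCRF". The exception is not limited to worsening. Protocol 8.2.1.2 makes a death related to an AE Grade 5, so a fatal outcome is also a grade change.

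**Definition.** Protocol 9.5 states: "A TEAE is an AE that emerges or worsens in the period from the first dose of study treatment", with the period ending 30 days after the last dose. SAP 7.3.1 (version 4.0) agrees: "any AE that emerges or worsens in the period from the first dose of study treatment to 30 days after the last dose".

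**Decision rule.** SAP 7.3.1 then says how status is determined: "The onset date of an AE will be compared to the first dose date and the last dose date plus 30 days". No comparison of grades is mentioned. Where a preferred term occurs more than once in a subject, "only the maximum grade observed for this PT will be used in summary of TEAEs by grade", and that maximum runs over TEAEs only.

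**Collection and follow-up.** Protocol 8.2.1 sets the recording period: "All AEs occurring in randomized subjects will be recorded in the eCRF from the time of ICF until 30 days after the last dose". The same section continues: "An AE will be followed until it is either resolved, has returned to baseline, or is determined to be a stable or chronic condition". Recording therefore starts before first dose, and an open event is followed past the point where recording formally ends.

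The only other rule for deriving TEAE status, SAP 6.2.1, deals with incomplete dates.

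**The concern.** Under the recording rule, one continuous event can become several records. Under the decision rule, each record is judged by its own start date. Neither document joins the records again or looks at the direction of the grade change.

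Two things can go wrong:

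- A pre-dose event that gets better after first dose produces a record with a post-dose onset. By date it is a TEAE; by definition it is not.
- A treatment-emergent event that becomes fatal after the window may have its death on a separate record outside the window. Neither document says whether the table of TEAEs resulting in death picks that death up.

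Safety is a secondary objective and TEAEs are a secondary endpoint (Protocol 2.2 and 3.2). Leaving the choice to whoever programs the analysis data means that the counts depend on an unstated decision.

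**Working it through.** The plan gives no figure on this point, so there is none to reproduce. The check is to run the written rules on invented records and compare the result with the definition.

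**Set-up (assumed).** First dose is day 1 and last dose is day 200, so the window runs from day 1 to day 200 + 30 = 230. Under the written rule, a record is a TEAE if its onset lies in days 1 to 230, and the reported grade is the maximum over those records. Under the proposed rule, records of one episode are linked. A grade-change record with onset in the window counts only if its grade exceeds the last pre-dose grade or the episode began in the window. A fatal outcome is attached to an episode that began in the window.

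| Case | Records (day: grade) | Written rule | Proposed rule |
|---|---|---|---|
| 1. Pre-dose, improving | −5: G3; 10: G2; 20: G1 | Two TEAE records, maximum G2 | Not a TEAE |
| 2. Pre-dose, worsening | −5: G1; 10: G3 | TEAE, G3 | TEAE, G3 |
| 3. Worsening inside the window | 50: G2; 60: G4 | TEAE, G4 | TEAE, G4 |
| 4. Non-fatal worsening after the window (last dose + 40) | 190: G2; 240: G4 | TEAE, G2 | TEAE, G2 (window kept) |
| 5. Fatal after the window (last dose + 35) | 220: G3; 235: G5 | TEAE, G3; the fatal record is not a TEAE | TEAE; death shown in the fatal-TEAE table, flagged as after day 30 |

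**Reading the cases.**

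- Case 1 is a plain error: nothing emerged or worsened after first dose, yet the subject is counted. By the same logic, an event falling from Grade 4 to Grade 3 after first dose would enter the table of Grade 3 or higher TEAEs.
- Cases 2 and 3 come out correctly as the plan stands.
- Case 4 follows from the stated window and is not an error.
- Case 5 is a gap. The documents do not say which record supplies the fatal outcome, so the death may or may not appear in the fatal-TEAE table. The event itself stays in the Grade 3 or higher table, because its first record is already Grade 3.

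**Who can be affected by case 1.** The event must arise or worsen between consent and first dose, still be open at first dose, and then drop a grade. Screening takes place within 30 days of dosing (Protocol Table 1), and conditions present before the study become AEs only if they worsen (Protocol 8.1.1). A subject counts once per preferred term, so one who also has a genuine TEAE of that term adds nothing to the subject count.

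**The case against.** The best defence is that the definition governs and the onset-date sentence merely implements it. A record created by a decrease neither emerges nor worsens, so a careful programmer would leave it out. That is a fair reading of intent, but the SAP gives only the date comparison as its method, and a programmer following it would flag the record.

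On late deaths, the defence is stronger. No text says that the fatal-TEAE table is built only from Grade 5 records, and an event with onset in the window that ends in death is naturally described as a fatal TEAE. Because AE recording formally stops at day 30, the second record may never be made. For serious events, Protocol 8.2.3.1 provides follow-up SAE reports. These points reduce the gap to one of unstated attribution. They do not close it, since no rule says how a late outcome reaches the table.

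A reader might go further and infer that every worsening after day 30 is wrongly lost. The documents do not support that. Both define the window in advance, and by then a subject may be on other anticancer therapy or on the opposite study drug in the extension study (Protocol 4.1), so carrying later grades back without limit would be debatable.

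The information also survives elsewhere. SAP 7.3.1 lists all AEs and SAEs by subject, and SAP 7.3.6 summarizes deaths during follow-up and lists deaths on study. Causes, however, are summarized only for on-treatment deaths.

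**Conclusion.** The point holds, with a narrow reach. Two statements are supported:

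- As written, the plan counts an improving pre-dose event as a TEAE, against its own definition.
- If a treatment-emergent event becomes fatal more than 30 days after last dose and is split into a new record, the death can be absent from the fatal-TEAE table. This depends on the new record being made and on how the table is programmed, neither of which is stated.

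The effect is limited to TEAE summary tables and is probably small. It cannot be sized, because the documents give no frequency for improving pre-dose events or for deaths from open events after day 30. A reader might try to derive a number of missing deaths from the phase 1 rate of serious pneumonia (15 of 55, 27%; Protocol 1.3.2.2). That would not be sound: 24 of those 55 subjects received 75 mg rather than the 25 mg used here, and the share dying late from a continuing event would have to be invented.

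**What to change.** Add a paragraph to SAP 7.3.1, carried into the ADaM specifications:

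1. Link contiguous records of the same term in a subject into one episode.
2. Flag a grade-change record with onset in the window as a TEAE only if its grade is higher than the last pre-dose grade, or if the episode itself began in the window.
3. For the fatal-TEAE table, attach a fatal outcome to the episode when its onset was in the window, and flag deaths after day 30 or after the start of new anticancer therapy. The flag lets a reader reconcile this table with the Grade 5 counts by maximum grade.
4. State that non-fatal worsening after last dose + 30 days stays outside the TEAE tables, as now defined.

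The cost is one SAP paragraph and a small programming task for the episode variable. No visit, treatment or efficacy analysis changes.
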